1. TTE
2. Hemodynamics
3. Metabolic parameters
4. Physiologic parameters and vital signs (including temperature)
5. Electrocardiogram
6. Blood sample for future research

Parameters collected during cooling protocol (18-24 hours after onset of cooling, prior to rewarming):

1. Hemodynamics
2. Metabolic parameters
3. Physiologic parameters and vital signs (body temperature measurements every 1-2 hours, as per the CCU policy)
4. Electrocardiogram

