5. TTE
6. Cumulative inotrope and vasopressor dosing (at the end of 24 hours of intervention)
7. Blood sample for future research

Parameters collected after rewarming (48-96 hours after completion of cooling protocol):

1. Hemodynamics
2. Metabolic parameters
3. Physiologic parameters and vital signs
4. Electrocardiogram

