5. TTE
6. Blood sample for future research

Endpoints

Primary safety endpoints:

1. Arrhythmia requiring medical therapy or therapy with temporary pacemaker
2. Bleeding requiring transfusions as a direct result of the cooling catheter insertion or secondary to resulting coagulopathy
3. Clinically important bloodstream infection, as confirmed with 2 positive blood cultures, or suspected sepsis in the absence of positive blood cultures with a sequential organ failure assessment (SOFA) score >2
4. Hypokalemia with potassium levels below 3.0mEq/L, not secondary to other identifiable causes

Secondary endpoints:

1. Hemodynamic changes during intervention period – Cardiac output/Cardiac Index, PCWP, SVR, mixed venous oxygen saturation (MVO₂), cardiac power index
2. Cumulative vasopressor and inotrope dose requirements (i.e. number of vasoactive and/or inotropic drugs used)
3. Echocardiographic % change in ejection fraction at 18-24 hours (from baseline)
4. In-hospital all-cause mortality

Procedures

Patients admitted to the Coronary Care unit (CCU) at the University of Chicago will be screened by the study investigators and the cardiology fellow on the CCU rotation. Patients meeting the inclusion criteria, as defined previously, will be identified and randomized after informed consent within 12 hours of presentation. Patients will be randomized to either TH plus standard medical care or to standard medical care alone. A pulmonary artery (PA) catheter will be placed at the bedside or in the Cardiac Cath lab if difficult anatomy is anticipated. As mentioned earlier, placement of a PA catheter is part of the standard of care for management of cardiogenic shock. Currently, patients who are admitted to the University of Chicago CCU with cardiogenic shock routinely undergo placement of PA catheter by the cardiology fellow in the CCU or in the cardiac cath lab. Data from the PA catheter is vital in initiating vasopressors/inotropes, assessing the response to the therapies, and possible need for escalation of therapy (i.e. mechanical support). In this study, patients in each arm will undergo PA catheter placement.

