administration of medications or a dialysis catheter for temporary dialysis. After successful insertion of the cooling catheter, it will be connected to the Thermogard XP® thermal regulation system. The Quattro® catheter functions as both a central venous triple lumen catheter as well as a cooling catheter. Cooling is achieved by circulating normal saline in a closed system through the catheter. The flow and temperature (range 4°C to 42°C) of the circulating saline serves as the heat exchange mechanism and is controlled by the external Thermoguard® thermal regulation system. The temperature is measured and adjustments are made by the thermal regulation system to automatically maintain target temperature. The target temperature is achieved within 2-3 hours of initiation of TH. Rewarming is accomplished using the same balloon catheter system and heat exchange occurs without infusion of any saline or fluids into the patient. In clinical trials, intravenous catheter based cooling system has been shown to achieve target temperature faster and maintain target temperature with more precision.^{12,14,15}

Medical therapy in both intervention and non-intervention groups will be based on the current recommendations for management of cardiogenic shock. This includes inotropic therapy (i.e. dobutamine or milrinone) for cardiac support, vasopressor therapy (i.e. norepinephrine, dopamine, phenylephrine, epinephrine) to achieve target blood pressure (mean arterial blood pressure \geq 60 mmHg), diuretics for volume removal, and mechanical circulatory support as clinically indicated. All patients included in this study will have pulmonary artery (PA) catheters inserted within 12 hours of randomization via either the internal jugular or femoral venous approach to monitor real-time hemodynamics. The clinicians in the CCU will use the data from PA catheters (cardiac output, mixed venous saturation, systemic vascular resistance, etc.) to guide therapy for both the intervention and non-intervention groups. The primary investigator of this study ([name]) will have no role in the clinical management of the patients.

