Laboratory, echocardiographic, and hemodynamic parameters will be obtained for patients prior to randomization, near the end of 24 hour cooling therapy, and after 48-96 hours post-randomization. Core temperature will be measured via either thermal tip at the end of a transurethral urinary catheter or endotracheal temperature probe in intubated patients. Rewarming will be accomplished at 0.3°C per hour until temperature reaches 37°C.

Target Enrollment and Study Duration

In this initial pilot study, we anticipate enrolling 20 patients to the study, 10 randomized to standard medical therapy and 10 patients randomized to standard medical therapy and 24 hours of TH. We anticipate completing enrollment within 6 months.

Statistical Methods

The three-dichotomous primary endpoints will be analyzed using a two-sample independent proportion test or a Fisher's exact test with a Bonferroni method continuity correction for multiple endpoints. Furthermore, numerical secondary endpoints will be presented as either

mean \pm standard deviation or median (interquartile range) based upon the distribution of the data. In addition, all numerical secondary endpoints will be assessed using two independent t tests or Mann-Whitney U test for comparisons. Categorical variables will be tested with chi-square tests of association or Fisher's exact tests. Differences will be considered significant using an alpha value of 0.05 for a two-sided test. Analyses will be performed using STATA MP Version 14 (College Station, TX).

Potential risks and benefits to subjects

A. Benefits:

There is mounting evidence that TH has positive effects on cardiac function. Multiple studies have suggested that TH may offer particular benefit in cardiogenic shock. In this prospective trial, the patients will be randomized to TH or standard medical care using simple randomization. With TH, we expect increased cardiac output, increased contractility, lower SVR, and higher cardiac power index which will lead to improved hemodynamics and potentially decreasing pressor requirements.

B. Risks:

Anticipated adverse events that could possibly occur during the study include, but are not limited to:

1. *Risks associated with TH*
 - a. Shivering
 - b. Arrhythmia
 - c. Coagulopathy with or without clinically significant bleeding
 - d. Hyperglycemia
 - e. Hypothermia
 - f. Electrolyte abnormalities
 - g. Infections
2. *Risks associated with cooling catheter insertion*
 - a. Bleeding
 - b. Infection

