Appendix 1 – Schedule of Study Activities

	Baseline	18-24 hours (after randomization)	48-96 hours (after randomization)	30-day Follow-Up	90-day Follow-Up
Informed Consent	X				
Review Medial History	X				
Review Medication History	X				
Height and Weight	X				
Vital Signs ^a	X	X	X		
Echocardiogram (TTE)	X	X	X		
Electrocardiogram (ECG)	X	X	X		
Hemodynamics ^b	X	X	X		
Blood Tests ^c	X	X	X		
Vasoactive Medication Dosing		X			
Potassium (pts randomized to cooling)		Q 4 hours			
Glucose Checks (pts randomized to cooling)		Q 1 hour			
Urine Output	X	X	X		
Randomization	X				
Adverse Events		X	X	X ^d	X ^d

^a blood pressure, heart rate, temperature (bladder or esophageal), respiratory rate

^b RA pressures, RV pressures, PA pressures, pulmonary capillary wedge pressure (PCWP), Fick cardiac output and cardiac index, systemic vascular resistance (SVR), pulmonary vascular resistance (PVR), cardiac power and cardiac power index, mixed venous saturation (MVO2)

^c serum lactate level, basic metabolic panel, hepatic function, coagulation parameters, complete blood count (CBC), arterial blood gas (ABG), and optional blood samples for future research

^d to be completed in clinic, when possible, or by phone

^e items to be charged to research during cooling include: meperidine

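### The two in-hospital visits run on conflicting clocks; read literally, the 18-24 h echocardiogram is lost when cooling stops early, and no completion rate is planned for the tolerability aim

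*Combined protocol and SAP*

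**What the plan says.** Three places give the timing of the second and third assessments.

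- Methods C (Timing of Data Collection): the second is "18-24 hours after onset of cooling, prior to rewarming"; the third is "48-96 hours after completion of cooling protocol".
- Appendix 1 (Schedule of Study Activities): the second column is headed "18-24 hours (after randomization", and the third, 48-96 h, also runs from randomization. Neither carries a cooling condition.
- Procedures, last paragraph: "near the end of 24 hour cooling therapy, and after 48-96 hours post-randomization", so cooling for the second and randomization for the third.

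Two secondary endpoints draw on the second assessment: "Echocardiographic % change in ejection fraction at 18-24 hours (from baseline", which names neither clock, and "Hemodynamic changes during intervention period". Neither carries a rewarming condition.

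The section on mitigating TH risks stops cooling and rewarms for persistent shivering, bradycardia needing a temporary pacemaker, arrhythmia attributed to hypothermia, and bleeding that is severe or does not respond to conservative measures. Statistical Methods plans two-group tests and gives neither an analysis set nor a rule for early stops.

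The Objective names tolerability as an aim. No primary or secondary endpoint counts completion of the 24 h. Expected events that end cooling are reported to the DSMB, and time in the temperature window is to be reported.

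**The concern.** Site staff have to choose a clock, and the documents do not choose it for them. For controls, the cooling clock does not exist.

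The choice matters most when cooling is stopped early. Under Appendix 1 the patient is still measured. Under a literal reading of Methods C, a patient already rewarmed before 18 h cannot be measured before rewarming, so no scheduled 18-24 h echocardiogram qualifies. That route to missing data exists only in the TH arm and is triggered by the treatment's own adverse effects. A comparison of those left would no longer compare the randomized groups.

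The tolerability gap is separate. A pilot with this aim should be able to say what share of patients got through 24 h of cooling. Treated arrhythmia and transfused bleeding overlap primary endpoints 1 and 2, but a stop for shivering alone appears in no endpoint.

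**Working it through.** The plan gives no figure here to reproduce. I put the windows on one clock.

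**Inputs.** Windows: Methods C, Procedures, Appendix 1. Rewarming: "Rewarming will be accomplished at 0.3°C per hour until temperature reaches 37°C". Time to target: "The target temperature is achieved within 2-3 hours of initiation of TH". Hours are after randomization. L is the lag from randomization to cooling onset, which the documents do not state. Procedures allows PA-catheter placement up to 12 h after randomization and describes cooling after catheter placement, so I show L from 0 to 12 h as an assumption. The 24 h of cooling are counted from onset.

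**Second visit.** Methods C window = 18+L to 24+L. Overlap with 18-24 h = max(0, 6-L). A visit at 18-24 h after randomization falls at 18-L to 24-L hours of cooling.

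| L (h) | Methods C window | Overlap (of 6 h) | Hours of cooling on the Appendix 1 clock |
|---|---|---|---|
| 0 | 18-24 | 6 | 18-24 |
| 1 | 19-25 | 5 | 17-23 |
| 3 | 21-27 | 3 | 15-21 |
| 12 | 30-36 | 0 | 6-12 |

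Planned cooling ends at 24+L, so the Appendix 1 visit never falls after planned rewarming begins. With a long lag, however, it is no longer near the end of cooling.

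**Late visit, L = 0.** Methods C: 24+48 to 24+96 = 72-120 h. Appendix 1 and Procedures: 48-96 h. Overlap: 96-72 = 24 of 48 h.

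**Is 48 h after rewarming?** Rewarming takes (37-34)/0.3 = 10.0 h to (37-32)/0.3 = 16.7 h. At L = 0, 37°C is reached at 34.0-40.7 h, which is 14 to 7.3 h before the 48 h mark. The 48 h mark stays after rewarming for L up to 48-24-16.7 = 7.3 h (from 32°C) or 48-24-10 = 14 h (from 34°C). At L = 12 h from 32°C, rewarming ends at 52.7 h, still inside 48-96 h. If the 24 h are counted from reaching target, cooling ends 2-3 h later and both lag limits fall by 2-3 h.

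**Early stop (assumed 33°C, same rewarming rate, L = 0).** Temperature = min(37, 33 + 0.3 × hours since stop).

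- Stopped at hour 12: 33 + 0.3×6 = 34.8°C at 18 h; 33 + 0.3×12 = 36.6°C at 24 h.
- Stopped at hour 6: 36.6°C at 18 h; 37°C at 24 h.

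Such patients can be measured, but partly or fully rewarmed.

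**How often?** No stop rate is given. Among 10 TH patients, the chance of at least one stop is 1-(1-p)^10: 40%, 65%, 89% and 97% for assumed p of 5%, 10%, 20% and 30%. Not every stop would come before 18 h.

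**Precision of a completion rate.** Exact 95% CI for the proportion stopped: 0/10, 0-30.8%; 1/10, 0.3-44.5%; 2/10, 2.5-55.6%. Simple randomization of 20 gives a TH arm of 6 to 14 with probability 95.9%; 0/6 gives 0-45.9% and 0/14 gives 0-23.2%.

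**The case against.** The case against is substantial. The only conflict that exists at zero lag is in the late visit, and no listed endpoint is defined there; Procedures and Appendix 1 already agree on it. The second visit conflicts only if cooling lags randomization. The before-rewarming phrase can be read as a timing instruction for the planned course; no text says to skip a patient whose cooling was stopped. PA-catheter monitoring continues throughout. The prospective 14-patient study described in the Background reports effective anti-shivering measures and no severe adverse events. Tolerability data are already captured through DSMB reporting and time in window.

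Most of this stands, and it limits the point. It does not remove it: the benign reading of the phrase is plausible but unwritten, the control clock is missing under Methods C, and captured data are not a planned completion rate.

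A reader might also infer that Appendix 1 should simply override everything. For the second visit the documents do not support that. Methods C and Procedures both tie it to cooling, and a long lag is permitted, though not established: Procedures also places baseline hemodynamics before randomization. At L = 12 h, a randomization clock would measure patients after only 6-12 h of cooling.

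**Conclusion.** The timing conflict is real and should be resolved before enrollment. Its consequence is conditional: EF values can be lost in the TH arm only, if Methods C is applied literally and a patient is rewarmed before 18 h. The hemodynamic endpoint is less exposed, because readings before the stop remain. Only secondary endpoints are touched.

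Three stronger readings are tempting and unsupported. The primary safety endpoints are not affected, since none is tied to these visits. A bias in favour of TH cannot be claimed, because neither stop rate nor direction is known. And the 18-24 h windows do not necessarily conflict: at L = 0 they coincide.

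The missing completion rate is a separate, smaller gap against a stated aim. The lag values, stop rates and 33°C starting temperature above are assumptions.

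**What to change.** 1. Set the late visit at 48-96 h after randomization in both arms, as Procedures and Appendix 1 already do, and later within that window if the patient is not yet at 37°C.
2. State that every living randomized patient has the 18-24 h TTE and hemodynamic assessment whether or not TH was stopped, and that the before-rewarming phrase is only a timing instruction for patients still being cooled. Compare arms as randomized, with the on-cooling subset as supportive.
3. State one second-visit clock for each arm. Either use 18-24 h after randomization in both arms, with cooling started promptly; or, closer to Methods C and Procedures, use 18-24 h after cooling onset in TH patients and 18-24 h after randomization in controls. In the second option the TH clock keeps running after an early stop, and randomization is used if cooling never starts. Record temperature, hours since cooling onset and hours since randomization at each assessment.
4. Report the proportion of TH patients completing 24 h, with hour and reason for each stop and an exact 95% CI on the actual arm size.

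The stopping rules do not change, and Appendix 1 already lists the assessments. The work is protocol wording and one descriptive table. The costs are a somewhat diluted as-randomized contrast; a between-arm difference of L hours in time since randomization if cooling onset is used, small if cooling starts promptly; a late visit sooner after rewarming than Methods C intended; and a completion rate that stays imprecise with about 10 patients.

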5. TTE
6. Cumulative inotrope and vasopressor dosing (at the end of 24 hours of intervention)
7. Blood sample for future research

Parameters collected after rewarming (48-96 hours after completion of cooling protocol):

1. Hemodynamics
2. Metabolic parameters
3. Physiologic parameters and vital signs
4. Electrocardiogram

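### Vasoactive drug use is scheduled as one 24-hour total, so it cannot be adjusted for use at entry, and a rebound on rewarming would not show in the scheduled data

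*Combined protocol and SAP*

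**What the plan says.** Secondary endpoint 2 is "Cumulative vasopressor and inotrope dose requirements", which a bracket then explains as the number of such drugs used. Methods B, item 7, instead lists cumulative doses. The Benefits section expects "improved hemodynamics and potentially decreasing pressor requirements".

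Methods C places one vasoactive item in the during-cooling list: "Cumulative inotrope and vasopressor dosing (at the end of 24 hours of intervention"). The baseline list has entries such as "Physiologic parameters and vital signs (including temperature") but no vasoactive item. The list headed "Parameters collected after rewarming (48-96 hours after completion of cooling protocol") has none either. In Appendix 1 the row "Vasoactive Medication Dosing" carries a single mark, which reads as the 18-24 hour column. The nearest baseline entry is "Review Medication History", with no dose or infusion rate specified.

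Procedures states: "Rewarming will be accomplished at 0.3°C per hour until temperature reaches 37°C". Statistical Methods compares numerical secondary endpoints between arms by t test or Mann-Whitney test and names no covariate.

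**The concern.** Need for vasopressors or inotropes is part of inclusion criterion 1d, and randomization may follow presentation by up to 12 hours. Patients can therefore enter on different drugs at different rates, or on none. A 24-hour total with no starting value mixes what the patient arrived on with what happened afterwards.

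The only record also closes as cooling ends, when the cooled arm begins to warm. If drug need rose again during rewarming, no scheduled item would capture it.

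Finally, clinicians in both arms, unblinded, adjust therapy to pulmonary artery catheter data. Cardiac index, vascular resistance and ejection fraction depend partly on the drugs running when they are measured. At baseline and at 48-96 hours no drug dose accompanies them. At 18-24 hours the accompanying figure is a running total, not the rate at the time of measurement.

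**Working it through.** **1. The schedule, item by item (Methods C and Appendix 1)**

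| Item | Baseline | 18-24 h | 48-96 h |
|---|---|---|---|
| Hemodynamics | yes | yes | yes |
| TTE | yes | yes | yes |
| ECG, blood tests, vital signs | yes | yes | yes |
| Vasoactive drug use | no | yes (24 h total) | no |

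The two places agree, so this is the design and not a slip in one table. Among the measures behind the physiologic secondary endpoints, only drug use has a single time point.

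**2. Length of the unrecorded rewarming period**

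Inputs: target 32-34°C, rate 0.3°C per hour, end point 37°C (Procedures). Time = (37 − T)/0.3.

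- From 34°C: 3/0.3 = 10.0 h.
- From 32°C: 5/0.3 = 16.7 h.

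If rewarming starts 24 h after cooling onset, it ends at 34.0 to 40.7 h. As a share of the 24 h dose window this is 10/24 = 42% to 16.7/24 = 69%.

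**3. Chance imbalance in drug use at entry**

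Inputs: 20 patients, 10 per arm (Target Enrollment), simple 1:1 randomization (Methods A). In units of the baseline SD, the difference in arm means has SD √(1/10 + 1/10) = 0.447.

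- P(|difference| > 0.3 SD) = 50%.
- P(|difference| > 0.5 SD) = 2[1 − Φ(0.5/0.447)] = 26%.
- P(|difference| > 0.8 SD) = 7%.

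These figures take an exact 10/10 split, which simple randomization of 20 gives with probability C(20,10)/2^20 = 17.6%. They would apply to any baseline variable and are not special to this one. What is specific here is that no scheduled dose would reveal the imbalance or allow adjustment.

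**4. What a baseline value could buy**

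The plan gives no power, effect size or SD for this endpoint, so it has no figure to reproduce. At two-sided 0.05 and 80% power, the detectable difference without adjustment is (1.960 + 0.842) × 0.447 = 1.25 SD by the normal approximation (1.32 SD for the t test). Adjusting for a baseline value with correlation ρ multiplies the variance by 1 − ρ² and the detectable difference by √(1 − ρ²). The documents give no ρ, so it is an assumption:

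| Assumed ρ | Residual variance | Detectable difference |
|---|---|---|
| 0.3 | 0.91 | 1.20 SD |
| 0.5 | 0.75 | 1.09 SD |
| 0.7 | 0.51 | 0.89 SD |
| 0.8 | 0.36 | 0.75 SD |

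The last column uses the normal approximation and ignores the degree of freedom spent on the covariate.

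**5. Timing of the third assessment**

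Methods C counts 48-96 h from the end of cooling, which is 24 + 48 = 72 to 24 + 96 = 120 h after cooling onset. Procedures and Appendix 1 count 48-96 h from randomization. Any later drug record tied to this visit inherits the conflict.

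**The case against.** The strongest reply is that endpoint 2 is a cumulative requirement compared between randomized arms, not a change from baseline. A lower total under hypothermia can be estimated without a starting value. This stands. A reader might infer that the trial cannot show reduced pressor need at all; the endpoint and the planned tests do not support that.

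A reader might also infer that missing baseline values bias the comparison. They do not: a randomized two-sample test already allows for chance imbalance. Baseline hemodynamics, lactate and blood pressure are collected too, so severity at entry is not invisible.

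Third, the endpoint is glossed as a drug count, and the plan names no common scale across drugs. A baseline dose SD is undefined until that is settled. This stands and shapes the fix. If a count is meant, drugs in use at entry may be partly recoverable from the medication review and the open-ended data list, but neither specifies rates or a time before randomization.

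Fourth, this is a small safety pilot. Its hemodynamic endpoints cover the intervention period, and none claims a lasting gain. Later deterioration is partly visible through repeat hemodynamics, lactate, TTE, adverse events and in-hospital mortality. That is fair, and nothing in the documents reports that cooling merely postpones drug need. But understanding physiologic effects is a stated aim, later hemodynamics are hard to read without doses, and the plan does not name pressor escalation as an adverse event.

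**Conclusion.** The point holds in a limited form. Drug use is scheduled once, as a 24-hour total, with nothing at entry and nothing during or after a 10 to 16.7 hour rewarming period. Within-patient change and rebound cannot be assessed from scheduled data, the 24-hour comparison cannot be baseline-adjusted, and the hemodynamics and ejection fraction at baseline and 48-96 hours lack concurrent doses.

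The missing baseline costs mainly precision and protection from chance imbalance (about a 26% chance of a gap above 0.5 SD with 10 per arm). The randomized test remains valid. The gain from adjustment depends wholly on the assumed correlation: 9% to 64% of the variance for ρ from 0.3 to 0.8. Whether a rebound occurs is unknown; the point is that the schedule would not show one. This is an inexpensive improvement to a secondary endpoint, and the primary safety endpoints are unaffected.

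**What to change.** - **Schedule.** In Methods C and Appendix 1, add abstraction from the medication record, in both arms, of vasoactive drugs, infusion rates and drug count immediately before randomization, through rewarming, and at the third assessment. Use the same clock windows from randomization in both arms, since controls have no cooling onset or rewarming to count from.
- **Endpoint.** State whether endpoint 2 is a drug count or a dose. If a dose, name one common scale.
- **Analysis.** Compare the 24-hour value adjusted for the baseline value. Report use after 24 hours descriptively beside it, and give concurrent rates with each hemodynamic and ejection fraction value.
- **Deaths.** Show deaths with every cumulative total, because early death lowers it. The Background cites in-hospital mortality as high as 50% in infarct-related shock. At that upper figure this is 5 of 10 per arm, though over the whole stay.
- **Timing.** Reconcile whether the third assessment is counted from completion of cooling or from randomization.

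Cost: chart abstraction for 20 monitored patients, with no new procedure or visit and no change to clinical management. The downsides are a few more data fields and an apparent benefit that may shrink once rewarming is included.
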